6.2 General Adverse Event Definitions

Following is a list of general AE definitions. For the purposes of this study, only SAEs, excluding elective procedures, as well as all AEs related to the operative site should be reported.

Adverse Event

An **AE** is any untoward medical occurrence, in a clinical investigation subject which changes the medical baseline of the subject, users or other persons. An AE can be an unfavorable and unintended sign, symptom or disease, whether or not related to the study device (AEs may also be referred to as complications). See Section 6.1, Reporting of Adverse Events, for the AE reporting requirements for this study.

NOTE 1 This definition includes events related to the investigational medical device or the comparator.

NOTE 2 This definition includes events related to the procedures involved.

NOTE 3 For users or other persons, this definition is restricted to events related to investigational medical devices.

Anticipated Adverse Event

An **anticipated AE** is an AE, of which the nature, severity or degree of incidence is known and identified in applicable product labeling, published literature or the study protocol. The list of anticipated events is provided in Section 12, Risk/Benefit Assessment.

Serious Adverse Event

A **SAE** meets one or more of the following definitions:

- led to death,
- led to serious deterioration in the health of the subject, that either resulted in
- a life-threatening illness or injury, or
- a permanent impairment of a body structure or a body function, or
- in-patient or prolonged hospitalization, or
- medical or surgical intervention to prevent life-threatening illness or injury or permanent impairment to a body structure or a body function,
- led to foetal distress, foetal death or a congenital abnormality or birth defect

NOTE Planned hospitalization for a pre-existing condition, or a procedure required by the protocol, without serious deterioration in health, is not considered a serious adverse event

Adverse Device Effect

An **adverse device effect (ADE)** is a negative change in the subject's health that may have been caused by, or associated with, the use of the device.

Unanticipated Adverse Device Effect

An **unanticipated adverse device effect** (UADE) is any serious adverse effect on health, safety or any life-threatening problem or death caused by, or associated with, a device if that effect is a problem or death not previously identified in nature, severity or degree of incidence, or any other unanticipated serious problem associated with a device and related to the rights, safety or welfare of subjects.

Device Deficiency

A **device deficiency** is an inadequacy of a medical device with respect to its identity, quality, durability, reliability, safety or performance. Device deficiencies that did not lead to an adverse event but could have led to a medical occurrence

- a) if either suitable action had not been taken,
- b) if intervention had not been made, or
- c) if circumstances had been less fortunate

NOTE Device deficiencies include malfunctions, use errors, and inadequate labelling.

6.3 Study Sponsor Notification by Investigator

Of reportable AEs, certain events must be submitted to Stryker Orthopaedics within 24 hours for timely notification:

Adverse events that require time sensitive reporting:

An adverse event should be reported to Stryker Orthopaedics Clinical Research either by telephone/fax/email within 24 hours after retrospective finding of the event if any of the following apply:

- The AE occurs intraoperatively or is related to the surgical procedure.
- The AE is considered by the investigator to be Simplex HV related or if the investigator is uncertain regarding the device related assessment;
- The Simplex HV relation requires a reoperation of the Triathlon total knee arthroplasty

At the time of the initial report, the following information should be provided:

 • Subject number • A description of the event • Date of onset • Current status 	
 • Whether study treatment was discontinued • Investigator assessment of the association between the event and the study treatment
---	--

Table 4 Initial AE report information

These reports will be evaluated by Stryker Orthopaedics to determine if a Product Inquiry (PI) is required.

6.3.1 Ethics Committee/Institutional Review Board Notification by Investigator

Reports of AEs (including follow-up information) must be submitted to the EC or IRB according to their specific requirements. Copies of each report and documentation of EC/IRB notification and receipt will be kept with the investigator's study files.

6.4 Medical Monitoring

It is the responsibility of the investigator to oversee the safety of the study at his/her center. This safety monitoring will include careful assessment and appropriate reporting of AEs, as previously noted. Stryker Orthopaedics will conduct formal investigations via the Product Surveillance Department of those AEs which are submitted through our PI System.

7 X-ray Analysis

[figure not shown]
7.1 Definition of Aseptic Loosening

X-rays will be collected at least at two years after surgery for independent analysis of radiolucency occurrence at implant-cement interface by an independent reviewer

[figure not shown]
- Radiolucency at implant-cement interface
 - Tibia A/P
 - Tibia lateral
 - Femur PS lateral or Femur CR lateral

Radiolucencies at the implant-cement interface more than 2 mm in all zones of a component is defined as aseptic loosening.

[figure not shown]
Zones Tibia A/P⁷

Zones Tibia Lateral⁷

Zones Femur PS Lateral⁷

Zones Femur CR Lateral⁷

[figure not shown]

Figure 2 Component zones

8 Data Management

8.1 Database

Paper based data will be collected at each center and entered into Stryker Orthopaedics's data base.

8.2 Confidentiality

This study will comply with the regional privacy rules. As such, Stryker Orthopaedics will only collect that information which is necessary to support the objectives of the clinical study. Stryker

Orthopaedics will take precautions to ensure that data received is de-identified as per regional privacy rules. In the case that some identified information is received, Stryker Orthopaedics will ensure that any identifying information is not publicly disclosed.

8.3 Source Documents

Source data include all information, original records of clinical findings, observations or other activities in a clinical study necessary for the reconstruction and evaluation of the study. Source data are contained in source documents. Examples of these original documents and data records include: hospital records, clinical and office charts, study worksheets, laboratory notes, memoranda, subject questionnaires, pharmacy dispensing records, recorded data from automated instruments, radiographs, subject files, and records kept at the pharmacy, at the laboratories and at medico-technical departments involved in the clinical study.

Monitors, defined further in Section 10, will be comparing the documentation in CRFs against source documents for adequacy. The monitors will seek to draw a reference between each data point on the CRF and the subject's chart. Every effort should be made to ensure complete source documentation.

8.4 Data Clarification Requests

If errors or omissions are noted by Stryker Orthopaedics upon review of the data entered into the CRFs, a data clarification request (DCR) will be sent to the center. Queries should be answered in a clear and comprehensible manner. If the clarification requires a change to study data, a copy of the DCR will be filed with the CRF.

8.5 Protocol Deviations

Any major deviation from this protocol will be recorded and must be reported to the EC/IRB by the investigational site according to their reporting procedures. Major protocol deviations for this study may include the following; this list may not be all-inclusive:

- Patient enrolled does not meet the inclusion/exclusion criteria
- Protocol specified study component(s) not implanted

8.6 Records Retention

It is the investigator's responsibility to retain study essential documents for two years after the date of the final report, or in the case of non-compliance, two years after the date of investigative center termination. These documents should be retained for a longer period if required by an agreement with Stryker.

9 Statistical Plan

9.1 Study Objectives

9.1.1 Objective Analysis

To evaluate the success rate of cemented Triathlon Total Knee components implanted using Simplex high viscosity bone cement (Simplex HV). Success is defined as absence of revision of cemented Triathlon Total Knee components implanted with Simplex HV for aseptic loosening at two years postoperative. 95% confidence interval of the success rate will be presented as well.

9.2 Safety

9.2.1 Safety Parameters

Safety parameters include all protocol-defined adverse events as well as revision and/or removal rates. For details regarding protocol-defined adverse events, see Section 6.1.

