6.1 Reporting of Adverse Events

The AE reporting requirements for this study are as follows:

- All AEs that meet the definition of serious
- All AEs related to the operative site, regardless of seriousness or time of occurrence

On retrospective review of postoperative data, investigators and study coordinators (SCs) will search the subject's hospital files as to whether they have seen a doctor for any reason, been hospitalized for any reason or have a current impediment to their function.

If it is determined upon this further investigation that a protocol-defined AE has occurred, the SC will be responsible to complete an AE CRF. If the event is related or uncertain related to the Triathlon TKA or to Simplex HV, the investigator will verify if the event has been reported to Stryker at time point of occurrence or will report at time point of data review at the latest. The event shall be reported to Stryker and to the IRB/EC, as required.

The following decision tree facilitates identification of AEs for which reporting is required under this study protocol:

[figure not shown]
Figure 1. Adverse Event Decision Tree

Figure 1 Adverse event decision tree

General Retrospective Review Findings

At screening for inclusion into the study, any clinically significant abnormality should be recorded as a preexisting condition and reported on the Demographics CRF. From the time of surgery forward, any new clinically significant findings or abnormalities that meet the definition of a protocol defined AE must also be recorded and documented as an AE until the end of the observation period or maximum at the five years follow-up.

Adverse Event Reporting Period

The study period during which AEs must be reported is defined as the period from the surgery to the last protocol specified follow-up.

During retrospective review of the subject's hospital files, information on protocol defined AEs shall be recorded in the AE CRF. The clinical course of each event should be followed until resolution or until it is determined at the end of the study that the AE will not resolve.

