9.2.2 Safety Analyses

The frequency and percentage of all protocol-defined adverse events will be tabulated.

For details regarding protocol-defined adverse events, see Section 6.1.

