9.4 Statistical Methodology

9.4.1 Data Summary

Descriptive statistics will be computed for all baseline conditions and demographic parameters. That is, for continuous data, the N, mean, median, standard deviation, minimum and maximum will be computed. For categorical data, the frequency will be computed. The data will be presented by appropriate subgroups (e.g., center, gender).

A Kaplan-Meier survivorship curve will be displayed for revision and/or removal of the Triathlon total knee arthroplasty cemented with Simplex HV for aseptic loosening.

A Kaplan-Meier survivorship curve will be displayed for all-cause revision and/or removal of the Triathlon total knee arthroplasty cemented with Simplex HV with Gentamicin for aseptic loosening.

Two year Kaplan-Meier success rate with 95% CI will be presented.

For all additional data collected that are not required for direct support of a study objective, data will be summarized according to follow-up. For parameters represented by continuous variables (e.g., ROM), the summaries will consist of the N, mean, median, standard deviation, minimum, and maximum values.

Documentation of statistical analyses utilizing SAS® software version 9.3 or higher will be maintained.

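### Revision and removal rates are listed as a safety parameter, but the plan specifies no clear all-cause revision analysis for non-medicated Simplex HV; revisions for other causes appear only within the adverse event tables, never as a rate

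*Combined protocol and SAP*

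**What the plan says.** Section 9.2.1 sets out the safety parameters: "Safety parameters include all protocol-defined adverse events as well as revision and/or removal rates". It limits the rates to no particular cause.

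The only analysis in section 9.2.2 is this: "The frequency and percentage of all protocol-defined adverse events will be tabulated".

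Section 9.4.1 provides two survivorship displays. For Simplex HV: "A Kaplan-Meier survivorship curve will be displayed for revision and/or removal of the Triathlon total knee arthroplasty cemented with Simplex HV for aseptic loosening". For the gentamicin cement, the curve is for "all-cause revision and/or removal of the Triathlon total knee arthroplasty cemented with Simplex HV with Gentamicin for aseptic loosening". It then adds a two-year Kaplan-Meier success rate with a 95% CI.

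The primary definition in section 9.1.1 is cause-specific: "Success is defined as absence of revision of cemented Triathlon Total Knee components implanted with Simplex HV for aseptic loosening at two years postoperative". It adds that a "95% confidence interval of the success rate will be presented as well".

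Section 6.1 makes all serious adverse events reportable, and also "All AEs related to the operative site, regardless of seriousness or time of occurrence". Exclusion A in section 5.1 excludes patients with revision surgery and does not say whether this means before or after the index operation.

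**The concern.** Section 9.2.1 treats revision and removal rates as an output separate from adverse events, but the analysis sections do not carry that output through without a restriction on cause.

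This matters because a cause-specific success rate depends on the cause recorded in the chart, and here the charts are read retrospectively. An all-cause rate does not depend on attribution, so it is the natural check. Without it, a reader cannot tell a high success rate that reflects few revisions from one that reflects revisions attributed to other causes. Section 1.1 itself names infection as the most common reason for failure of knee arthroplasty, ahead of loosening, with wear and instability after that. By the protocol's own account, the leading cause of failure lies outside the primary endpoint.

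**Working it through.** The plan gives no figure to reproduce. The 100 cases per cement were set by the regulatory body (section 9.4.2), and no revision rate is assumed anywhere. The check is therefore to trace the outcome through the plan and then illustrate its size.

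**Tracing a knee revised for a cause other than aseptic loosening**

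| Place | What happens to it |
|---|---|
| 9.2.1 | Falls within the revision and removal rates, which carry no cause restriction |
| 9.2.2 | Enters the adverse event table if reportable; no revision rate is specified |
| 9.4.1, Simplex HV curve | Not an event, because the curve is limited to aseptic loosening |
| 9.4.1, gentamicin curve | Undetermined, because the sentence states both scopes |
| 9.1.1, success rate | Not a failure: a success in a crude proportion, probably censored in Kaplan-Meier; no rule is stated |
| AE form, Appendix B | The coded revision or removal option, with its revision date, is for aseptic loosening only; other surgery on the operated side is free text |

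The AE form classifies events by MedDRA category. A table built from it would count infections or other events rather than revised knees, and would give no 24-month estimate or interval.

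**Illustration of size (assumed counts)**

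Inputs: n = 100 knees of one cement (section 9.4.2), and an assumed 2 aseptic-loosening revisions plus 1 to 4 other first revisions by 24 months. With x knees free of the event, the proportion is x/n. The exact (Clopper-Pearson) 95% limits are the 0.025 quantile of Beta(x, n − x + 1) and the 0.975 quantile of Beta(x + 1, n − x).

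| Failures counted | Success | Exact 95% CI |
|---|---|---|
| 2 (aseptic loosening only) | 98/100 = 98.0% | 93.0 to 99.8 |
| 3 (plus 1 other) | 97/100 = 97.0% | 91.5 to 99.4 |
| 4 (plus 2 other) | 96/100 = 96.0% | 90.1 to 98.9 |
| 6 (plus 4 other) | 94/100 = 94.0% | 87.4 to 97.8 |

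The point estimate falls by 98.0 − 97.0 = 1.0 to 98.0 − 94.0 = 4.0 points. The lower limit falls by 93.0 − 91.5 = 1.5 to 93.0 − 87.4 = 5.6 points.

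**Does censoring in Kaplan-Meier reveal the difference?** Suppose the other revisions all come before the two aseptic ones and nothing else is censored. With 1 other, the aseptic-loosening estimate is (98/99)(97/98) = 97/99 = 98.0%. With 4 others it is (95/96)(94/95) = 94/96 = 97.9%. The all-cause figures remain 97.0% and 94.0%. Censoring barely moves the cause-specific rate.

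**Zero aseptic revisions.** The crude primary figure is 100% (96.4 to 100) whether there are 0 or 5 other revisions. With 5, the all-cause figure is 95/100 = 95.0% (88.7 to 98.4).

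**Would the gap arise in practice?** The chance of at least one other-cause revision in 100 knees is 1 − (1 − p)^100. For assumed risks p of 1%, 2%, 3% and 5% it is 63%, 87%, 95% and 99%.

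**The case against.** Several objections have force.

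- **Such revisions are not invisible.** A reader might infer that these knees show up only as primary successes. The documents do not support that. Sections 6.1 and 6.2 would normally make such a revision reportable as a serious or operative-site event, and 9.2.2 tabulates those. The follow-up form has a box for reasons other than aseptic loosening, and the AE form has an entry for other operative treatment. This stands: what is missing is the rate, not every trace of the event.
- **They are not necessarily counted as successes.** In a cause-specific Kaplan-Meier analysis the knee would usually be censored at revision. Exclusion A, read literally, could remove it altogether, and both analysis populations in 9.4.4 are limited to non-censored subjects. This stands too; what remains is that the primary rate never counts the knee as a failure.
- **The term all-cause does not appear in 9.2.1.** Correct. It is the fair reading of an unqualified phrase, not the wording.
- **General clauses might cover it.** The synopsis plans frequencies and percentages for categorical variables, and 9.4.1 plans summaries of additional data by follow-up. Neither names revision, gives its scope or calls for a rate over time, so they do not supply the analysis. It is fair to say that a Kaplan-Meier estimate with an interval asks for more than the bare rates that 9.2.1 lists.
- **The gap is not confined to one cement.** A reader might infer that the gentamicin half of the study is covered and only the other half is not. The gentamicin sentence contradicts itself, so that cannot be relied on. Section 3.1 also uses the name Simplex HV for both versions, which leaves the scope of the first curve less than certain.

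**Conclusion.** The point holds in a limited form. Section 9.2.1 names revision and removal rates with no cause restriction, and no later section clearly delivers an all-cause rate for the non-medicated cement. For the gentamicin cement the planned curve is self-contradictory. Revisions for other causes would appear within the adverse event tabulation but not as a rate, and the primary rate would not register them as failures.

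The size of 1 to 4 points per 100 knees is illustrative. It rests on assumed counts and on crude proportions with exact intervals, which are not the Kaplan-Meier intervals the plan calls for. The omission does not invalidate the primary analysis. It leaves a listed safety parameter without a clear analysis and removes the simplest check on attribution of cause, so it should be corrected.

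**What to change.** Add to section 9.2.2, in substance: for each cement separately, time from the index surgery to first revision or removal for any cause will be analysed by Kaplan-Meier, with the 24-month estimate and 95% CI, together with a count of revisions by cause taken from the AE form, including its free-text entry for other operative treatment. Show these results next to the aseptic-loosening success rate.

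State in section 5.1 that revision of the index knee after the study surgery does not trigger exclusion A. Without this, an all-cause rate could look falsely perfect because revised knees had been excluded.

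Also state in 9.4.1 how a revision for another cause is handled in the aseptic-loosening analysis, and reconcile the two scopes in the gentamicin sentence.

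The cost is a few sentences, one extra Kaplan-Meier run per cement, and some manual coding of cause and date from free text and charts. The sponsor also accepts a figure beside the primary rate that may be less favourable.

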9.2.2 Safety Analyses

The frequency and percentage of all protocol-defined adverse events will be tabulated.

For details regarding protocol-defined adverse events, see Section 6.1.

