2.3 Number of Subjects

Cases will be enrolled until a total of 100 cases with Simplex HV non-medicated and 100 cases with Simplex HV with Gentamicin were observed and collected. Depending on the hospital

standard of care, a site may only enroll subjects receiving Simplex HV non-medicated and another site may only enroll subjects receiving Simplex HV with Gentamicin.

3 Device Description

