5.1 Inclusion/Exclusion Criteria

Inclusion Criteria:

- A. The Patient is age 18 or over at time of study device implantation
- B. Patients who have undergone primary Triathlon Total Knee Arthroplasty in which Simplex HV/Simplex HV Gentamicin was indicated for fixation and used on label
- C. Patients who have been followed for at least 24 months postoperatively

Exclusion Criteria:

- A. Patients who have undergone revision surgery
- B. Patients who have undergone bilateral Knee Arthroplasty
- C. Patients contraindicated for either the devices implanted, or the cement used, according to medical history review and instructions for use
- D. Patient has a cementless tibial baseplate.
- E. Patient has an active or suspected latent infection in or about the affected knee joint
- F. Patient has muscle loss or neuromuscular impairment in the affected limb that would create an unjustifiable risk
- G. Patient is immunologically suppressed or receiving steroids in excess of normal physiological requirements (e.g. > 30 days)
- H. Patient has a known hypersensitivity to any of the cements constituents or in patients with severe renal failure
- I. Patient is a prisoner

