5.4 Post-operative Data Collection

Data collection at 24 months (+ 2 months) postoperatively and optional at 5 years postoperative.

- Knee Society Score (KSS)
- Oxford Knee Score (OKS)
- X-ray collection for independent analysis
 - A/P view
 - Lateral view
- Elective surgery since study surgery
- Post-operative Adverse event or device deficiency

6 Adverse Events

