9.4.3 Interim Analyses

No interim analysis is planned. Retrospective data up to five years will be analyzed.

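### The adverse event percentage in section 9.2.2 has no time basis, although event capture runs from 24 months to as long as five years depending on the subject

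*Combined protocol and SAP*

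**What the plan says.** The AE analysis in section 9.2.2 is a single sentence: "The frequency and percentage of all protocol-defined adverse events will be tabulated". It names no window, period split or time-to-event estimate.

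The collection rules do not supply a common window:

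- Section 6.1 defines the reporting period: "The study period during which AEs must be reported is defined as the period from the surgery to the last protocol specified follow-up". It also has new findings recorded "until the end of the observation period or maximum at the five years follow-up".
- Section 5.1 sets the minimum through inclusion criterion C: "Patients who have been followed for at least 24 months postoperatively".
- Section 5.4 schedules data collection at 24 (+2) months and "optional at 5 years postoperative".
- Table 1 has a column from 27 months to 5 years. There KSS, OKS and X-ray are optional, while adverse events are marked as per protocol.
- Section 9.4.3 adds: "Retrospective data up to five years will be analyzed".

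Complications are a secondary objective in the synopsis. On enrolment, section 2.3 notes that "a site may only enroll subjects receiving Simplex HV non-medicated" and that another site may enrol only the gentamicin version.

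**The concern.** A percentage of subjects with an event has a meaning only together with the time over which events could be counted. Here that time may be about two years for one subject and five for another, and the plan divides by everyone without distinguishing them. The result cannot be read as a risk at either time point, nor set beside a published 24-month or 5-year figure.

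The mix of follow-up lengths may also differ between sites. If a site contributes only one cement, a difference in the length of record review becomes a difference between cement groups. A reader who sees the two groups of 100 side by side could take that for a safety difference. The primary endpoint does not have this problem, because it is fixed at two years (section 9.1.1).

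**Working it through.** **1. Is a time basis set anywhere else?** Four places could supply one, and none does.

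- Section 9.4.1 plans Kaplan-Meier curves, but only for revision or removal. Other AEs are not covered.
- Section 9.4.1 also summarises some data by follow-up, but limits this to additional data not needed for a study objective. Complications are a secondary objective, so on its wording the sentence does not reach them.
- Section 9.4.4 defines the safety population without a time point.
- Table 1 shows when AEs are collected, not how they are tabulated.

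**2. Inputs for the size.** The documents give no expected AE rate, no share of subjects with late follow-up and no time pattern of events, so there is no plan figure to reproduce. From the documents: minimum follow-up 24 months, maximum 60 months. Assumed: a true 24-month risk *p* of 10%, with 2%, 5% and 20% as alternatives; a share *f* of subjects followed to 60 months, the rest to 24; and a late hazard equal to *k* times the early hazard.

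**3. Constant hazard (*k* = 1).** The 5-year risk is 1 − (1 − *p*)^(60/24).

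For *p* = 10%: 1 − 0.90^2.5 = 1 − 0.7684 = 23.2%.

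The crude percentage is (1 − *f*) × *p* + *f* × (5-year risk):

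| Share to 5 years | Calculation | Crude percentage |
|---|---|---|
| 25% | 0.75 × 10% + 0.25 × 23.16% | 13.3% |
| 50% | 0.50 × 10% + 0.50 × 23.16% | 16.6% |
| 100% | 23.16% | 23.2% |

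With everyone at five years, assumed 24-month risks of 2%, 5% and 20% become 4.9%, 12.0% and 42.8%.

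**4. Front-loaded hazard, everyone at five years.** The 36 months after month 24 are 1.5 times the first 24, so the crude percentage is 1 − (1 − *p*)^(1 + 1.5*k*). For *p* = 10%:

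| Late hazard relative to early | Calculation | Crude percentage |
|---|---|---|
| 0.5 | 1 − 0.90^1.75 | 16.8% |
| 0.25 | 1 − 0.90^1.375 | 13.5% |
| 0.1 | 1 − 0.90^1.15 | 11.4% |

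**5. The two-month visit window.** With a constant hazard, counting to 26 rather than 24 months gives 1 − 0.90^(26/24) = 10.8%. The window in the schedule is therefore a minor matter; follow-up beyond it drives the effect.

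**6. With a common cut-off.** If events are counted to 24 months in every subject, the expected percentage is *p* whatever the later follow-up, and two groups with the same true risk show an expected difference of zero.

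**The case against.** The best defence is that section 9.2.2 is silent rather than wrong. It does not require one pooled percentage or rule out tabulation by period, Table 1 schedules AEs in separate columns, and the dates needed for a 24-month cut are collected, so the cut can be made at analysis. It is true that no information is lost. But a table produced from the sentence as it stands has no time basis, and a window chosen after the data are seen is weaker than one set beforehand.

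Several stronger readings are tempting, and the documents do not support them:

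- **Late AE capture is optional.** Section 5.4 may suggest this, but Table 1 marks late AEs as per protocol and reserves optional for KSS, OKS and X-ray. What varies is how long subjects are followed.
- **The plan compares the cements on a biased measure.** No between-cement test or contrast is planned, section 9.2.2 does not say that the AE table is split by cement, and section 2.3 says only that a site may use one cement.
- **The AE table will be shown by center.** The subgroup sentence in section 9.4.1 closes the paragraph on baseline and demographic data. Nothing extends it to AEs.
- **Equal cements would read 10% against 23%.** That needs a constant hazard, and one group followed entirely to five years with none of the other. Several complications listed in section 12.2 are peri-operative, which makes some front-loading plausible.
- **The Kaplan-Meier results are affected too.** The planned summary is the two-year estimate, which differences in follow-up after 24 months do not change.

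**Conclusion.** The point holds as a fault of the AE table. Followed as written, section 9.2.2 yields a percentage that is neither a 24-month nor a 5-year risk and that depends on how many subjects have later follow-up.

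Its size cannot be fixed from the documents. In the scenarios with a true 24-month risk of 10%, the crude figure lies between 11.4% and 23.2%. The upper end needs a constant hazard with everyone at five years; the lower end has a late hazard one tenth of the early one. If few subjects go beyond 26 months, the distortion is small under any hazard pattern considered here.

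The harm is to the description of complications and to informal reading across the two cement groups. That second harm also requires follow-up length to differ by cement, which the possibility of one-cement sites allows but the documents do not establish. Revision and removal have their own time-to-event display, so the gap concerns the other AEs.

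**What to change.** Amend section 9.2.2 in two parts:

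1. Make the main AE table the number and percentage of subjects with an event whose onset falls between surgery and 24 (+2) months, shown for each cement group. Inclusion criterion C requires at least 24 months of follow-up, so the denominator can be all subjects in the group.
2. List events with later onset in a separate table, with the number of subjects still under observation, and do not merge them into the main percentage.

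The cost is a few lines of SAP wording and one extra table. The forms in Appendix B already record the AE start date, the surgery date and the follow-up examination date.

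A rate per person-year is not recommended in place of the cut-off. It would still depend on follow-up length if the hazard falls after month 24. A late rate restricted to subjects with late data would also be open to selection, and the forms show no clear end-of-observation date from which to compute person-time.
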